9.3.2. Baseline questionnaire completion

After eligibility has been confirmed and written consent obtained, and prior to randomisation, patients will be provided with a questionnaire booklet to be completed during the visit. The baseline questionnaire booklet will comprise the following questions;

- Demographic and socio-economic questions
- Pre-injury Olerud and Molander (1984) ankle score (see section 7.1)
- EQ-5D-5L (see section 7.2)

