9.3.4. Randomisation

Following completion of baseline information collection, a member of the research team will randomise the participant to one of the two treatment groups; Removable support boot, or plaster.

Patients will be randomised in order to minimise systematic bias, using a secure web-based system designed and maintained by the Peninsula Clinical Trials Unit

(PenCTU) according to the Unit's standard operating procedures. Computer generated randomisation codes prepared by the PenCTU will be kept secure, with access restricted to the data management team at the PenCTU. Participants will be allocated to the support boot group (intervention) or to the plaster group (control) in a 1:1 ratio, using random, even, block sizes between 2 and 8 to generate the allocation sequence and achieve balance in the numbers of participants allocated to each group. Randomisation will be stratified by site. The web-based randomisation system will be accessed securely via unique log-in details provided to each local team member by the CTU. The system ensures that allocation is appropriately concealed until the point of randomisation.

Upon randomisation, each participant will be assigned a unique Trial Number which will be used as the principal identifier on trial data collection forms and questionnaires. The research team member will disclose the allocation to the participant and will ensure the allocation is followed as described below.

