12. STATISTICS AND DATA ANALYSIS

12.1. Sample Size Calculation

The study is powered to detect a 10-point difference in ankle score since patient and public involvement indicated that walking without aids/getting back to work were the most important issues. A change from support with a stick/crutch to no support and a change to getting back to normal work/activities of daily life from simpler or part-time work are both associated with a 10-point change on the Olerud and Molander¹⁴ subjective scale (primary outcome).

An estimate of standard deviation of the ankle score six weeks post-surgery was derived from an audit of 18 patients having plaster casts at Poole Hospital. This figure of 21.9 is very similar in magnitude to those reported in the Cochrane review¹³. Based on an unpaired t-test with two groups of equal size, assuming 90% power, a two-sided 0.05 significance level, a standard deviation of 21.9 and a mean difference of 10 points between the plaster and boot groups, a total sample size of 204 (102 in each group) is required²¹. The study will over-recruit by 20%²² to allow for non-responders, or missing data, not to contribute data to the main analysis. However it is anticipated that the true percentage will be reduced by offering flexible methods of completion; either online, post or by phone. As the study progresses, the percentage with missing primary outcome data will be monitored and discussed at regular trial management group meetings and reductions/increases in over-recruitment will be made accordingly so that the target of 204 with completed data is met.

The study will aim to recruit 246 patients in total (123 in each group) over a 2 year recruitment period.

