Instead of implementing stratification of age and fracture complexity at randomisation (which in any case could be problematic if there is a large number of strata with a relatively small sample size), the potential issue of imbalance in age and fracture complexity between the two arms of the trial will be addressed by adjusting (stratifying) for the covariates of age (as a continuous variable) and fracture complexity in the analysis. Thus the proposed analysis of the primary outcome, for example, will use multiple regression and, in addition to treatment arm, include the pre-specified variables of study site, age and fracture complexity.

Two groups are proposed regarding fracture complexity: Simple fibular fracture and comminuted fracture. If the fibular fracture has a single fracture line with two discrete fragments only, it comprises a 'simple' fracture. If the fibula has more than one fracture line and therefore more than two discrete fragments that require accurate reduction to achieve stability, it comprises a comminuted fracture. The pattern and complexity of the fracture can influence the choice of hardware used by the surgeon to achieve stability. Simple fractures are fixed with unlocked plates whereas complex fractures can require more sophisticated and expensive locked plates.

The pre-baseline measure is collected retrospectively and so has not been included in the primary analysis. By ten weeks post-baseline, it is anticipated that both groups will be similar on the primary outcome, and so this has not been included in an overall repeated measures type analysis. The five week post-baseline data collection period is the critical period, as this is when it is anticipated that the group who had boots will have a greater level of function^{3,6}.

Some additional analyses (including sensitivity analyses) on primary outcome will also be conducted:

(a) It is acknowledged that some participants (in either group) will leave the 4 week appointment with a plaster cast or boot, and so will complete the scale whilst still wearing the plaster/ boot. In a supplementary sensitivity analysis these participants will be excluded from the analysis to see if the results change.

(b) Pre-injury Olerud and Molander scale will be included as a covariate.

(c) Whether or not the patient had a medial malleolar fracture will be included as a covariate

(d) Any baseline variables that appear, by chance, to differ between the groups will be added in as covariates.

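### The reason given for leaving the pre-injury ankle score out of the primary model does not hold: it is recorded before randomisation, so adjusting for it costs only possible precision, never validity

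*Protocol*

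**What the plan says.** Section 12.2.2 compares mean ankle score at five weeks between arms by multiple regression on arm, site, age (continuous) and fracture complexity. On the pre-injury ankle score it says "The pre-baseline measure is collected retrospectively and so has not been included in the primary analysis", and gives no other ground. That score enters as a covariate only in additional analysis (b).

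On timing, section 9.3.2 says "After eligibility has been confirmed and written consent obtained, and prior to randomisation, patients will be provided with a questionnaire booklet". The booklet holds the demographic questions, the pre-injury ankle score and EQ-5D-5L. Section 9.3.4 places randomisation after baseline collection.

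Baseline EQ-5D-5L is not in the primary model and the protocol does not say why. Sections 12.2.3 and 12.4 do adjust QALYs for baseline utility, alongside site, age and fracture complexity.

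Additional analysis (d) reads "Any baseline variables that appear, by chance, to differ between the groups will be added in as covariates". Section 12.2.3 carries analyses (b) to (e) over to the secondary outcomes.

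**The concern.** Retrospective recall is a sound reason for caution when the recall could be coloured by the treatment received. Here it cannot be: the patient answers before anyone knows the allocation. The stated ground therefore does not justify excluding the score from the primary model.

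The protocol is also uneven in how it treats these measures. Section 12.2.2 trusts the recalled score enough to compare the arms on change from pre-injury to ten weeks, and on the proportion at least 10 points worse. Those uses ask more of the score than serving as a covariate. Baseline utility is accepted as a covariate for QALYs but not for the ankle score.

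Analysis (d) is the weaker way to deal with imbalance. It sets no criterion for a difference, and section 12.2.1 rules out baseline significance tests, so the choice would be made by eye. An observed imbalance says nothing about whether a variable predicts the outcome.

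At stake is the width of the interval around the headline estimate, and a covariate set that can be defended as chosen before the data were seen.

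**Working it through.** **Inputs.** Section 12.1 plans a two-sample t-test with equal arms, "assuming 90% power, a two-sided 0.05 significance level, a standard deviation of 21.9 and a mean difference of 10 points". The resulting target there is 204 completers, 102 per arm. Section 9.3.4: 1:1 allocation. No document figure exists for the correlation r between the baseline measures and the five-week score, so r is an assumption. It means the partial correlation, given the site, age and complexity terms already in the model. The calculation uses the planning SD of 21.9 as the SD before the extra covariates are added.

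**Step 1: reproduce the plan's figure.** Normal approximation: n per arm = 2 × (1.960 + 1.282)² × 21.9² / 10² = 100.8, so 101 per arm and 202 in total. The t-test version gives 101.76, so 102 per arm and 204 in total, with power 90.1%. The stated 204 is correct, and no covariate entered it.

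**Step 2: what a covariate adds.** Residual SD = 21.9 × √(1 − r²). The 95% interval half-width is 1.96 × residual SD × √(2/102). Power and required N use the t-test.

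| r (assumed) | Fall in variance (r²) | Residual SD | Power at 102 per arm | Total N for 90% | Half-width, points |
|---|---|---|---|---|---|
| 0 | 0% | 21.90 | 90.1% | 204 | 6.0 |
| 0.1 | 1% | 21.79 | 90.3% | 202 | 6.0 |
| 0.2 | 4% | 21.46 | 91.2% | 196 | 5.9 |
| 0.3 | 9% | 20.89 | 92.5% | 186 | 5.7 |
| 0.4 | 16% | 20.07 | 94.3% | 172 | 5.5 |
| 0.5 | 25% | 18.97 | 96.3% | 154 | 5.2 |

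**Step 3: does a badly recalled covariate do harm?** Simulation of 4,000 trials per setting, 102 per arm, true difference 10. The pre-injury score was recalled with error (SD 5 points), capped at 100 and measured before allocation.

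| Correlation of recalled score with outcome | Mean adjusted estimate | SE unadjusted | SE adjusted |
|---|---|---|---|
| 0 | 9.95 | 3.11 | 3.10 |
| about 0.23 | 9.97 | 3.02 | 2.95 |
| about 0.39 | 9.96 | 3.09 | 2.82 |

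The Monte Carlo error of each mean is about 3.1/√4000 = 0.05, so the estimates agree with 10. A covariate that predicts nothing cost nothing visible. One that predicts something reduced the standard error by roughly the amount in step 2.

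**The case against.** The strongest reply is that the protocol never claims adjustment would bias the result. It says only that the measure is recalled, and a noisy covariate is a fair candidate for a sensitivity analysis. The adjusted model is already pre-specified as (b), so the dispute is over which of two valid models is labelled primary. The gain may also be slight. Section 12.2.1 fixes one item worth 20 of the 100 baseline points at its maximum for everyone, and section 8.2 excludes patients who could not walk before injury, so scores may cluster near the top.

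Much of this stands. No correlation is given, and for the pre-injury score alone r of 0.1 to 0.2 is plausible, worth about one power point at most. It does not rescue the stated reason: imprecise recall limits the benefit, but it is no argument against inclusion when inclusion costs nothing.

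Two practical objections also stand and must be met. Section 12.2 bars imputation in the main effectiveness analyses, which leaves a missing baseline covariate without a rule. Section 12.2.3 leaves the EQ-5D-5L value set open between final five-level scores and the crosswalk.

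A reader might infer more than the documents support:
- **The omission biases the result or leaves the trial underpowered.** It does neither. The 204 was computed without adjustment.
- **EQ-5D-5L was left out because it is retrospective.** That reason is given only for the pre-injury score, and EQ-5D-5L is not labelled as a pre-injury measure.
- **Analysis (d) shapes the primary result.** It is supplementary; the primary covariates are fixed.
- **Power should be judged at 197 completers** (80% of 246, from section 12.1). That section undertakes to adjust recruitment until 204 have complete data. The synopsis gives 276 recruits, of whom 80% is about 221.

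**Conclusion.** The rationale in section 12.2.2 is unsound and should be corrected, and a precision gain that needs no extra patients or data is left unused in the primary model. Its size is about r² of the residual variance: 1% to 25% for an assumed partial correlation of 0.1 to 0.5. At 102 per arm the half-width goes from 6.0 to between 6.0 and 5.2 points. Below about r = 0.2 the gain is marginal; from about 0.3 it is worth having. Adding EQ-5D-5L, answered two weeks after surgery, may raise the joint correlation above that of the pre-injury score alone, but nothing in the protocol lets one say by how much. This is an efficiency improvement. The planned primary analysis is valid, and the sample size does not depend on the change.

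**What to change.** - **Primary model.** Five-week ankle score on arm, site, age (continuous), fracture complexity, pre-injury ankle score and baseline EQ-5D-5L utility. Delete the sentence that excludes the pre-injury score. Keep the present model as the sensitivity analysis in place of (b).
- **Value set.** Name the EQ-5D-5L value set before any analysis, since the primary result would then use it.
- **Missing covariates.** State that the no-imputation rule in section 12.2 concerns outcomes, so that a rare missing baseline covariate may be filled by its mean without reference to arm. Section 9.3.7 has staff check the baseline booklet for gaps, so few should be missing.
- **Analysis (d).** Replace it with a list fixed in advance on prognostic grounds, drawn from baseline items already collected (for example sex and BMI). Medial malleolar fracture is already covered by (c).

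The cost is wording in the protocol and the matching text of the SAP, agreed before analysis. Nothing changes in data collection, recruitment or the target of 204.

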3. INTRODUCTION

Approximately two million ankle fractures occur annually in the United Kingdom affecting 3.6% of the population, 75% in under 60 year olds¹, of which a high proportion need surgical fixation, with considerable cost to the National Health Service. Indeed, 7.2% of all fractures admitted to Poole Hospital are ankle fractures and 197 underwent surgical fixation in 2011² illustrating the scale of the issue (audit data suggest 104 in Basingstoke in 2012 and 76-80 in six month periods in 2009 and 2010 respectively in Portsmouth). Ankle fractures are a cause of short-term and sometimes long-term disability and pain. These injuries frequently require many weeks off work with subsequent economic consequences³. Six weeks of immobilisation in plaster is frequently advocated for all ankle fractures *not* requiring surgery. It is also recognised practice to immobilise a broken ankle after surgery for comfort, support and to allow the wound to heal. This tends to be with a plaster because it is cheap and readily available in the operating theatre and has been used for decades.

However, there has been no consensus for the management of ankle fractures post-operatively for those ankle fractures that need surgical fixation. Therefore, current treatment is not standardised in many Trusts in the National Health Service. There is evidence to suggest that removing plasters and wearing removable boots that allow early weight-bearing and range of movement of the ankle, maximises rehabilitation potential.

A number of studies have investigated the benefits of early weight-bearing and mobilisation following ankle fracture fixation. Early return to function should be the principal goal following surgical management³. Traditionally, patients have been managed in a plaster cast and have been strictly non-weight-bearing (hopping on their unaffected leg).

However, immobilisation can result in reduced range of movement and muscle deterioration⁴⁻⁶. Early mobilisation of ankles following open reduction and surgical internal fixation provides short-term benefits in improved range of movement, reduced swelling, pain, an earlier return to work, improved patient satisfaction, and better ankle function⁷.

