8.2. Exclusion Criteria

Patients who meet any of the following criteria will be excluded from study participation:

- Under 16 years old (skeletal immature).
- Poor skin condition at operation site.
- Serious concomitant disease (e.g. stroke, osteoporosis, arthritis).
- Diabetic neuropathy/other sensory neuropathy (lack of sensation).
- Non-ambulatory prior to injury.
- Active leg ulceration.
- Patients who are unable to understand the study information or unable to complete the outcome questionnaires.
- Surgeon concerned about quality of fixation/integrity of wound.
- Fracture requiring further stabilisation in/around the ankle (e.g. syndesmosis).
- Open ankle fracture (bone broken through skin).
- Participant is a participant in other concurrent interventional research which may over-burden the participant or confound data collection.
- Concomitant injuries which will have a confounding effect on rehabilitation in the opinion of the investigator.

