(e) The effectiveness of the intervention may vary across different subgroups (strata) of patients (e.g. age and fracture complexity). Therefore for each outcome

supplementary statistical analyses are proposed in which it is tested whether there is a statistical interaction between age and treatment arm and between fracture complexity and treatment arm. It is however acknowledged that statistical power will be reduced for these significance tests and they will be considered to be exploratory. Age will be grouped as: under 65 years of age at the time of fracture and 65 + years.

(f) The main analysis will use an “intention to treat” approach. As a supplementary analysis two sets of “per protocol” analyses will also be conducted. In the first of these, patients will be analysed according to the method (boot or plaster) that they actually wore. If patients crossed over from one to the other during the 4 week period they will be excluded from the per protocol analysis. If patients didn’t wear the boot/plaster for the full 4 weeks they will be excluded. In the second analysis participants will additionally be excluded if they didn’t perform the exercises recommended. Thus if they performed the exercises less than once per day they will be excluded

(g) Data on primary outcome completed outside of the 3-10 day window will be included in the analysis

(h) The robustness of the results to missing data will be assessed by repeating the analysis incorporating the imputed values that will be derived as part of the economic analysis (see section 12.4)

The study will also compare the ten week Olerud and Molander Ankle score between groups to check whether any differences still remain at 10 weeks.

To see whether patients in both groups have returned to pre-injury levels of function we will calculate the mean difference (95% CI) between pre-injury and 10 week values for each group, and the proportion of patients whose score is worse by 10 points or more. These statistics will also be compared between groups.

12.2.3. Secondary outcomes:

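### The exploratory treatment-by-age test cuts age at 65 without a stated reason, although the primary model keeps age continuous; this avoidably loses roughly 40–60% of the age information if the effect changes linearly with age

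*Protocol*

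**What the plan says.** Protocol section 12.2.2 handles possible imbalance in age and fracture complexity by "adjusting (stratifying) for the covariates of age (as a continuous variable) and fracture complexity in the analysis". Study site is also in that model.

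Additional analysis (e) in the same section raises the possibility that the effect differs between types of patient. For each outcome "it is tested whether there is a statistical interaction between age and treatment arm and between fracture complexity and treatment arm". The scale of age is then fixed: "Age will be grouped as: under 65 years of age at the time of fracture and 65 + years". Just before that, the protocol limits the weight of the result: "It is however acknowledged that statistical power will be reduced for these significance tests and they will be considered to be exploratory". Section 12.2.3 carries analyses (b) to (e) over to the secondary outcomes, some of which are binary or categorical and analysed by logistic regression.

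No reason is given for the cut at 65 or for the change of scale. The expected share of participants aged 65 or older is not stated. The one age figure is in section 3, on UK ankle fractures in general: "75% in under 60 year olds".

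**The concern.** Splitting a continuous variable for an interaction test treats everyone on one side of the cut as alike, so here a 20-year-old and a 64-year-old, and places any change in effect at a single age. Information within each group is lost, and the loss grows as the split becomes more uneven. The protocol's own figure points to an uneven split at 65, and the exclusions in section 8.2, which include "Serious concomitant disease (e.g. stroke, osteoporosis, arthritis" as examples, probably make it more uneven.

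Two things are at stake. A real gradient of effect with age is more likely to go undetected than it need be. And the 65+ estimate, resting on perhaps 14 to 21 patients per arm, would be imprecise enough for a chance result to attract attention. The protocol fixes the cut for every outcome, so an analysis plan that follows it inherits the cut.

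**Working it through.** **Inputs from Protocol section 12.1.** "assuming 90% power, a two-sided 0.05 significance level", with "a standard deviation of 21.9 and a mean difference of 10 points between the plaster and boot groups"; 204 analysable patients, 102 per arm, allocated 1:1.

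**Reproducing the plan's figure.** An unpaired t-test with difference 10, SD 21.9, 90% power and two-sided 0.05 needs 101.76 per arm. This rounds up to 102, or 204 in total, with power 0.901. The stated 204 is correct and is used as N below.

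**Share aged 65 or older (assumption).** The protocol does not give it. If 75% of participants are under 60, then 25% are 60 or older and fewer than that are 65 or older. The ceiling is therefore 25%, or 51 of 204. Several age distributions were set to the 75% figure (the two-peaked one came to 78% under 60):

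| Assumed age distribution | Share 65+ | Age information kept by the cut |
|---|---|---|
| Normal, SD 12 to 22 years | 13.8–18.4% | 41–47% |
| Normal truncated to 16–90 years | 15.6–18.6% | 45–55% |
| Uniform 16–60, then uniform 60–80 | 18.7% | 50% |
| Two-peaked | 17.0% | 54% |
| Uniform 16–60, then uniform 60–90 | 20.9% | 61% |

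The plausible range is about 14–21%, or 28–43 of 204.

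**Information kept.** If the treatment effect is linear in age, the fraction kept by a two-group split is the squared correlation between age and the 65+ indicator. For normal age with 65+ share p this is φ(z)²/[p(1−p)], where z is the standard normal point with p above it. For uniform age it is 3p(1−p). The shapes in the table keep 41–61%, a loss of 39–59%. For detecting a linear interaction, this is like analysing about 83 to 124 of the 204 patients (204 × 0.408 and 204 × 0.609).

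**Precision of the split at 65.** The interaction is the treatment difference in the older group minus that in the younger group. With 1:1 allocation within each group:

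SE = 21.9 × √[4/(204p) + 4/(204(1−p))]

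The difference detectable with 80% power is (1.96 + 0.84) × SE. Power for a 10-point interaction is Φ(10/SE − 1.96). With continuous age and a truly linear effect, 10/SE is divided by the square root of the fraction kept. Here a 10-point interaction means a gradient that would make the two age groups differ by 10 points on average. The last two columns assume normal age.

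| 65+ share | Patients 65+ | SE | Detectable, 80% power | Power for 10 points, cut | Fraction kept | Power for 10 points, continuous |
|---|---|---|---|---|---|---|
| 14% | 29 | 8.8 | 24.8 | 20% | 41% | 42% |
| 16% | 33 | 8.4 | 23.4 | 22% | 44% | 44% |
| 21% | 43 | 7.5 | 21.1 | 26% | 50% | 47% |
| 25% (ceiling) | 51 | 7.1 | 19.8 | 29% | 54% | 49% |

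An even split would have SE 6.1 and 37% power for 10 points. Much of the weakness therefore comes from the sample size, and the cut adds to it.

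**The case against.** The strongest reply is that the protocol already places the right limits on this test. It calls it exploratory and concedes low power, and a cut fixed in advance at least rules out choosing one from the data. This stands, and it is why the point carries little weight. It does not explain why a further, avoidable loss should be accepted.

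A second reply is that the two uses of age differ. Adjustment for chance imbalance and a look at subgroups may legitimately use different scales. This also stands: the passages do not contradict each other, and the primary estimate, its standard error and the sample size are untouched.

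Third, continuous age does not rescue the test. Power for a 10-point interaction would still be under 50% in every row above, even with a perfectly linear effect. If the effect really changed at an older age, a cut might lose little. Both points are correct.

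Two stronger readings are tempting but unsupported. A reader might infer that at least half of the age information is always lost. That needs a 65+ share of about 21% or less together with roughly normal or uniform age; at the 25% ceiling with normal age the loss is 46%, and the other shapes give as little as 39%. A reader might also take the older group to be very small, say 10% (about 20 of 204). With normal age, 75% under 60 and only 10% aged 65+ would require an SD of about 8 years around a mean of about 54, which is implausibly narrow for a trial recruiting from age 16. The exclusions might bring the share that low, but nothing in the protocol quantifies their effect.

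**Conclusion.** The point holds as a low-weight improvement to an exploratory analysis. The protocol fixes a less efficient method than its own primary model already uses for age, and gives no reason. With 14–21% of 204 completers aged 65 or older, the interaction standard error is about 7.5–9 points. The test then reaches 80% power only for effect differences of about 21–25 points, more than twice the 10-point difference the trial is powered to detect.

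The loss of roughly 40–60% of the age information rests on three assumptions: that a figure for UK ankle fractures in general carries over to surgically fixed fractures meeting this trial's criteria, that age follows one of the shapes tried, and that the treatment effect changes linearly with age. It would be wrong to conclude that an age-dependent effect is bound to be missed under the present plan, or would be found under the alternative. At 16% aged 65+, power for a 10-point interaction would go from about 22% to about 44%.

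**What to change.** In section 12.2.2(e), replace the sentence that groups age with a test of treatment by continuous age. Add a restricted cubic spline check for the continuous outcomes only, because a spline interaction may be unstable for sparse binary outcomes such as individual complications. Report the estimated boot–plaster difference with 95% CI at a few prespecified ages, for example 30, 50 and 70. Keep the split at 65 as a descriptive table without a significance test, and retain the exploratory label.

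The cost is a short wording change and a little more reporting. Age is already collected and already in the model as continuous. The downside is that a linear term may miss a threshold effect; the descriptive table and, for continuous outcomes, the spline check help to show one.

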7.7. Mobilisation and adherence to exercise

Data will be collected to assess whether participants have adhered to instructions to complete exercises. Physiotherapists will make recommendations for participants to exercise and mobilise their ankle as often in a day as pain allows based on an

advice leaflet specific to their treatment allocation (recommended at least 3 times a day.) Compliance will be defined as once per day or more.

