10.2. Plaster Cast

The plaster cast used will be a standard below knee rigid plaster cast shell with soft lining to provide support in a fixed position to the ankle. The plaster cast is rigid enough to support weight-bearing and is custom built for the patient.

The plaster group will also receive a trial specific advice leaflet on plaster care/mobilisation of free joints. The leaflet will provide illustrated instructions of the following exercises: Toe flexion/extension, Static quads and Straight leg raises. Patients will be encouraged to mobilise their ankle as often in a day as pain allows (recommended at least 3 times a day.)

Participants will be advised on gait re-education with crutches and will progress to weight-bearing as able.

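### The two supplementary analyses called per-protocol in section 12.2.2(f) group patients by the device worn, so they are an as-treated/per-protocol hybrid open to selection bias in either direction

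*Protocol*

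**What the plan says.** The main analysis is by intention to treat (Protocol sections 12.2 and 12.2.2(f)). Section 12.2.2(f) adds two supplementary analyses of the primary outcome under a per-protocol label.

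- **First set.** The grouping rule is that "patients will be analysed according to the method (boot or plaster) that they actually wore". Patients who changed device during the four weeks are excluded, as are those who did not wear the device for the full period.
- **Second set.** The same rules apply, with one more: "Thus if they performed the exercises less than once per day they will be excluded". This matches section 7.7: "Compliance will be defined as once per day or more".

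The exercises behind that rule differ by arm. The boot leaflet (section 10.1) lists straight leg raises, active ankle movements, a calf stretch and resisted plantarflexion. The plaster leaflet (section 10.2) lists toe movements, static quadriceps work and straight leg raises. In both arms the frequency advice depends on pain. For plaster it reads: "Patients will be encouraged to mobilise their ankle as often in a day as pain allows".

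**The concern.** A per-protocol analysis restricts each randomised arm to the patients who followed the plan. It does not move anyone between arms. Under the rule as written, a patient randomised to boot who was put in plaster and stayed in it for four weeks counts as a plaster patient. That contradicts the label, and no other section corrects it.

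Both sets also select patients on what happened after randomisation, in a trial where patients and clinicians know the allocation (section 5.2). If the reason for wearing the other device, or for exercising little, is linked to how well the ankle is doing, the groups compared are no longer the randomised groups. Because exercise is advised as far as pain permits, a patient below once a day may be one with a poor early course. Because the exercises differ, the same threshold may select different patients in each arm.

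At stake is how the intention-to-treat result is read. Readers will take an analysis labelled per-protocol as support for it or as a challenge to it. Unlike the interaction tests in (e), (f) carries no statement that it is exploratory.

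**Working it through.** **Inputs from the protocol.** Section 12.1: "assuming 90% power, a two-sided 0.05 significance level, a standard deviation of 21.9 and a mean difference of 10 points"; "a total sample size of 204 (102 in each group) is required". Section 9.3.4 gives 1:1 allocation.

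**Inputs assumed.** The protocol gives no rate for wearing the non-allocated device, no rate for low exercise, and no correlation of either with the score. These are varied below.

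**The plan's own figure.** The normal approximation gives n = 2(1.960 + 1.282)² × 21.9² / 10² = 100.8, so 101 per arm. The exact t-test calculation gives 102 per arm with power 90.1%. The stated 204 reproduces. The standard error of the comparison is 21.9 × √(2/102) = 3.07 points.

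**Model.** There is no true effect. A latent standard normal behaviour variable has correlation ρ with the score. Covariates are ignored. Differences are boot minus plaster.

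**Exercise exclusion (second set only).** Excluding the lowest share p of an arm raises the mean of the latent variable in those who remain by λ(p) = φ(z_p)/(1 − p), where z_p is the normal quantile at p. The bias is ρ × 21.9 × [λ(p boot) − λ(p plaster)], with ρ equal in both arms.

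| Excluded boot / plaster | λ boot − λ plaster | ρ = 0.3 | ρ = 0.5 |
|---|---|---|---|
| 15% / 5% | 0.2743 − 0.1086 = 0.1657 | +1.1 | +1.8 |
| 25% / 10% | 0.4237 − 0.1950 = 0.2287 | +1.5 | +2.5 |
| 5% / 15% | −0.1657 | −1.1 | −1.8 |
| 10% / 25% | −0.2287 | −1.5 | −2.5 |

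Equal shares with equal ρ give exactly zero. In simulation (102 per arm, 4,000 trials per scenario), 30% excluded in both arms at ρ = 0.5 gave +0.1 points and 5.7% rejections at two-sided 0.05. The range in the table is not a ceiling. With 30% excluded in boot at ρ = 0.5 and 10% in plaster at ρ = 0, the formula gives 0.5 × 21.9 × 0.4967 = 5.4. The simulation gave +5.4, and −5.5 when the arms were swapped.

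**Grouping by device worn (both sets).** Assume that the boot patients with the poorest outlook wear plaster throughout and the plaster patients with the best outlook wear the boot, a share p in each arm. The boot group then has latent mean (1 − p)λ(p) + φ(z_p) = 2φ(z_p), and the plaster group has the opposite. The bias is 4φ(z_p) × ρ × 21.9. At p = 10% and ρ = 0.3 this is 4 × 0.1755 × 0.3 × 21.9 = 4.6. If every patient stays in the randomised arm and deviators are only excluded, it is 2λ(p) × ρ × 21.9 = 2 × 0.1950 × 0.3 × 21.9 = 2.6.

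Simulated means, with the rejection rate at two-sided 0.05:

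| Wearing the other device throughout | ρ | By device worn | Randomised arm kept, deviators excluded |
|---|---|---|---|
| 10% per arm | 0 | 0.0 (4.9%) | 0.0 (5.1%) |
| 10% boot to plaster only | 0.3 | +2.3 (11.0%) | +1.3 (6.4%) |
| 5% per arm | 0.3 | +2.6 (14.1%) | +1.3 (7.4%) |
| 10% per arm | 0.3 | +4.7 (32.8%) | +2.6 (13.8%) |
| 10% per arm | 0.5 | +7.6 (70.6%) | +4.2 (27.0%) |

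Intention to treat stayed within about 0.1 points of zero, with about 5% rejections, in every scenario. Reversing the assumed link with prognosis reverses the sign of the device-worn bias.

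**The case against.** The main objections are these.

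- **These analyses are supplementary.** Intention to treat is fixed as the main analysis. This stands: a reader might infer that the primary result is compromised, and it is not.
- **Few patients may be moved.** Section 9.3.4 makes the research team responsible for seeing that the allocation is followed, the device is fitted right after randomisation, and patients who change device or stop early are excluded rather than moved. This stands. Only those in the other device throughout change group, and their number may be small.
- **Only the second set uses exercise.** It would be wrong to say that both sets drop low exercisers.
- **The direction is not known.** A reader might infer that the analyses favour the boot, because its exercises load the ankle. The protocol does not support that. The advice on pain has the same form in both arms, nothing indicates that boot patients will miss the threshold more often, and swapped rates favour plaster by the same amount.
- **The exercise bias is modest.** At the tabulated rates, 1.1 to 2.5 points is below one standard error (3.07). That is fair, although the device-worn figures can exceed it.
- **An instrumental-variable estimate need not replace (f).** It assumes that randomisation acts only through the device received. The arms also differ in leaflets and exercises taught, and the outcome is patient-reported and unblinded. This stands, so such an estimate is an option and not a requirement.

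None of this answers the central point: the label says per-protocol and the rule moves patients between groups.

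**Conclusion.** The point holds as a defect in a supplementary analysis that the protocol itself fixes. Section 12.2.2(f) describes an as-treated/per-protocol hybrid under a per-protocol name, and its second set adds selection on a post-randomisation behaviour tied to partly different exercises in each arm.

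With no true effect, the bias is zero if deviation is unrelated to prognosis; for the exercise rule it is also zero if selection acts equally in both arms. It is about 1 to 2.5 points, in either direction, for the exercise rule at 15%/5% to 25%/10% excluded and ρ of 0.3 to 0.5. It is about 2 to 8 points for grouping by device worn, at 5 to 10% non-allocated wear and the same ρ. Against the 10-point target difference, the upper figure would matter to a reader. All of these rates and correlations are assumptions, so they show what could happen and do not predict it. Neither the sample size nor the main result changes.

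**What to change.** Reword section 12.2.2(f), and carry the wording into the SAP, before any analysis:

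1. In any analysis called per-protocol, keep every patient in the randomised arm and exclude those who did not wear the allocated device. Never count them in the other arm. If grouping by device worn is wanted, call it as-treated.
2. Label both sets exploratory and prone to selection bias, as (e) already does for the interaction tests. Step 1 reduces the bias but does not remove it (+4.7 to +2.6 points in the 10%, ρ = 0.3 scenario).
3. Report by arm the numbers excluded, with reasons, and the exercise adherence.
4. Optionally, add a complier-average causal effect estimate with randomised arm as the instrument. State its exclusion restriction, how receipt of the device is defined under partial wear, and that its interval will be wider.

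Separately, section 10.2 encourages plaster patients to mobilise the ankle while describing a cast that holds it in a fixed position. These statements must be reconciled. The exercise rule can still operate on the exercises listed in the leaflet.

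The cost is a wording change. The same data are used, adherence is already recorded at the 4-week visit, and no sample size figure moves. Patients in the non-allocated device throughout drop out of the per-protocol set, so it becomes slightly smaller.
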